6.4 Secondary endpoint

1. Expression of key immune system markers (genes and proteins) and immune cell population frequency and activation status
2. Number and type of bacterial species in stool and mouth samples.
3. Severity of NAFLD - based on histology and Fibroscan (transient elastography)
4. In a subset of patients, non-invasive assessment of liver function and metabolic control once 5% to 7% weight loss is achieved
5. Measure of quality of life at baseline and once achieved 5% to 7% weight loss
6. Healthcare utilization; populated from healthcare records

7. Study population

Participants will be identified from outpatient clinics of Bariatric, Gastroenterology, and Hepatology services at Homerton and King College Hospitals in addition to Gastroenterology outpatients from the Barts Health NHS Trust. An additional cohort will be recruited from the community weight loss program, Fit For Life, run in Tower Hamlets and Waltham Forest at the Bromley by Bow Centre.

Healthy control participants will be identified from patients undergoing outpatient assessment, gastroscopy or surgery for other non-malignant gastrointestinal disorders at hospital sites. Participants will have the opportunity to discuss the study with a member of the research team when they receive a copy of the patient information sheet. Only adults 18 years of age and above and not classified as a vulnerable adult will be recruited. Most participants will only need to attend one or two study visits including consent.

7.1 Inclusion criteria

- Age \geq 18 years
- Confirmed non-alcoholic Fatty liver disease (diagnosed clinically, radiologically or histologically)
- If diabetic, Diagnosed with Type 2 Diabetes Mellitus

OR

- Healthy Control: no diagnosis of any liver condition including NAFLD
 - NAFLD excluded by Fibroscan Controlled Attenuation Parameter (CAP) score of <222 dB/m

7.2 Exclusion criteria

- Unwilling or unable to give informed consent
- Type 1 Diabetes Mellitus
- Other form of liver disease (other than NAFLD)
 - Viral hepatitis, Auto-immune hepatitis, primary sclerosing cholangitis, primary biliary cholangitis, haemochromatosis, Sarcoidosis, cystic fibrosis, sickle cell disease
- Taking medication associated with liver dysfunction (except methotrexate)
- Auto-immune disease which in the investigator's opinion may confound immune profiling
- Concomitant immunosuppressive medications (except methotrexate, short course oral steroids or inhaled corticosteroids)
- Currently pregnant
- Any major organ transplant (excluding corneal or hair transplant)
- Regular alcohol intake greater than 14 units a week for female participants and 21 units a week for male participants

8. Study design

This observational study will invite individuals from hospital outpatients (Gastroenterology and Bariatric services), community weight loss program or academic institutions associated with hospital sites to form the NAFLD and healthy control participants respectively. We plan to recruit 153 participants over an expected 24 month period. Opening this study at two bariatric surgery services we would expect to meet recruitment targets. However, if opportunistic recruitment does not meet expectations we will collaborate with other centres with whom we have existing relations (Imperial College and University College, London).

Participants will be approached at routine clinic appointments if pre-screened to meet study inclusion criteria. Community participants will have a short presentation at the beginning of their weight loss program where the study will be explained by one of

the research team with the opportunity to ask questions. All potential participants will be given a copy of the PIS at this visit. A combined screening/first study visit will then be arranged, usually by telephone or e-mail. Following consent, bariatric surgery participants or healthy control participants undergoing elective abdominal surgery will have a second study visit defined as the day of surgery for tissue sample collection. Patients will be asked to monitor their weight and when they reach 95% of starting weight, they will be asked to contact the study team to arrange a visit. All participants will have a final study visit once they have attained 5% to 7% weight loss, this is expected to be between one to six months after baseline visit. Participants who do not achieve at least 5% weight loss 6 months after the baseline visit will also be asked to attend the visit.

Healthy control patients will be identified from patients undergoing outpatient assessment, gastroscopy or elective surgery for other non-malignant gastrointestinal disorders at NHS organisations associated with the study; Kings College Hospital, Barts Health NHS Trust and Homerton University Hospital.

In order to exclude significant hepatic steatosis in healthy control participants and ensure study eligibility we will utilise the Controlled Attenuation Parameter (CAP) function of the Fibroscan. This is particularly important due to the recognised poor negative predictive value of liver ultrasound.³⁷ This will be carried out at the participant's screening visit after informed consent.

There is range of published cut-off values to determine the presence of hepatic steatosis (215 dB/m- 268 dB/m).³⁷⁻⁴⁰ For the purposes of our study we have utilised the data from a recent publication comparing CAP score in 349 individuals with NAFLD and 437 healthy controls as determined by proton-magnetic resonance spectroscopy.³⁷ At the cut-off of 222 dB/m, the sensitivity, specificity, positive predictive value and negative predictive value of CAP, for diagnosing NAFLD, were 93.1%, 45.1%, 57.5% and 89.1%, respectively.³⁷ This indicates it to be an appropriate cut-off for our study.

9. Study procedures

At the first study visit a researcher will obtain informed consent and determine that the participant meets all study inclusion and exclusion criteria to proceed. Consent will include agreeing to access NHS databases for medical information and access to existing tissue samples surplus to clinical requirements. The study researcher will guide the participant through the consent form and case report form (CRF). This will also incorporate the Short Form (36) Health Survey (SF-36) as a measure of participant self-reported health status. This is in addition to medical and drug history in addition to smoking, alcohol, dietary and exercise data. The same assessment will take place at the final study visit, once they have achieved 5% to 7% weight loss.

Data collection will include:

1. History and examination: family history, smoking and drinking habits, past medical history, drug history, demographics (race, gender, age) and life-style (quality of life, dietary, exercise and sleeping habits).
2. Anthropometric measurement including body weight, body height, waist circumference and Body Mass Index (BMI).
3. Transient elastography (Fibroscan)
4. Fasted clinical blood tests including liver function and metabolic profile.
5. Fasted research blood tests - 55mls (3 tablespoons) extra.
6. Urine, saliva and stool samples
7. Optional fine needle aspiration of the liver

Every effort will be made to arrange all study procedures at each time point in a single visit, however, if this is not possible, participants have the option to return at an alternative date for that component / those components.

If a participant is undergoing bariatric or upper gastrointestinal surgery for a non-malignant indication, a study investigator or research nurse will attend the day of their surgery and collect the tissue samples: liver and adipose tissue and gut tissue (if their operation includes bowel resection) having consented previously. All participants with NAFLD will be offered a follow up visit once they have achieved 5% to 7% weight loss with repeat assessment of immune-profile and liver specific tests. Additional consent pertaining to fine needle liver aspirate will be obtained immediately prior to this procedure. The standard NHS consent form will be used for this.

Study procedures by visit

Study intervention	Visit 1	Visit 2 (Surgical & biopsy participants only)	Visit 3 (5%-7% weight loss achieved)
Informed Consent	X		
Screening	X		
Medical history	X	X	X
Questionnaires	X		X
Blood sample	X	X	X
Urine, stool, saliva samples	X	X	X
Liver Fibroscan	X		X
Liver Fine Needle Aspiration (Optional)	X		X
Liver Biopsy sample (If already clinically indicated)		X	
Intra-abdominal tissue sampling (At time of planned surgery)		X	

If the study procedures identify a significant liver abnormality, elevated liver function tests or elevated Fibroscan score. We will ensure the participant is informed by one of the study investigators and referred for further investigation and management within a liver clinic at either Barts Health or Kings College Hospital.

If a participant wishes to fully, or partially, withdraw from the study, they will be asked if they wish to have existing data and samples to be destroyed or whether they can be still used for the purposes of the study. Withdrawal of consent will be documented in the participants CRF.

10. Assessment and management of risk

We do not expect any significant additional risk to participants within this study. Blood samples would amount to no more than 55mls in total, substantially less than taken at time of a blood donation, approximately 400mls. Fresh tissue samples will only be collected from participants undergoing a planned procedure such as a liver biopsy for existing clinical purposes or bariatric surgery. A large review of the safety of liver 3806 biopsies without direct visualisation but guided by ultrasound revealed an exceptionally low rate of haemorrhagic complication 0.32% or hypovolaemic shock 0.11%.³³ Furthermore, the Lille bariatric cohort did not report any significant risks associated with the 1496 intra-operative liver biopsies performed within their study.¹⁹ Tissue samples taken at time of surgery have minimal risk as they are performed under direct vision of the operating surgeon with ability to ensure haemostasis post biopsy.

Participants will have an optional fine needle aspiration of their liver at baseline and at follow up, once attaining 5% to 7% weight loss. This procedure has been in use for more than 20 years as a research and clinical tool with better safety profile than standard liver biopsy.³⁴ A recent study revealed safe repeated fine needle aspiration from the same study participants with the only adverse event reported as pain post procedure requiring simple analgesia in two cases after 39 fine needle aspirates.³⁵ Furthermore, another research group has reported no serious complications in a series of more than 500 fine needle liver aspirates.³⁶ In this study, liver FNA will be only undertaken by individuals with adequate prior experience to minimise risk to participants.

We expect small risk to study researchers undertaking analysis of biological samples from this study. Standard mitigating precautions including personal protective equipment, sealed containers opened only in fume hoods within containment level 2 laboratory facilities will be adhered to. Further information can be found in section 15 regarding laboratories. All research staff dealing with samples will have to demonstrate up to date safety training either from their employing NHS trust or academic institution.

11. Statistical considerations

Patients undergoing assessment for bariatric surgery will predominantly be classified as obese, BMI $>30\text{Kg/m}^2$ ($>27.5\text{Kg/m}^2$ for South Asian patients) or more likely severely obese, BMI greater than 35Kg/m^2 . It is recognised that up to 90% of obese individuals will have concurrent NAFLD.¹ A recent meta-analysis reports the incidence of NASH among NAFLD patients to be 59.1%⁴¹ although in a bariatric cohort with more risk factors, a higher proportion is expected. A previous NAFLD study in 109 predominantly Caucasian bariatric patients revealed that almost 90% of patients undergoing bariatric surgery had evidence of NASH with at least stage 1 (out of 4) fibrosis¹⁹.

In this exploratory, basic science observational project, formal power calculations are not possible. However similar work by our group suggests that 40 patients in each of the following groups: NASH with mild fibrosis (stages 0-1) and significant fibrosis (stages 2-4) will be informative. Given that we cannot determine the stage of disease before surgery, and assuming a conservative NASH rate of 75% of all patients and a

relatively even split of patients into the two categories and 20 healthy control participants we estimate that a total sample size of 153 will enable us to recruit with 20% contingency for dropout.

Techniques involved in analysis of biological samples will include flow cytometry, quantitative polymerase chain reaction, RNA sequencing of immune cell populations, 16S ribosomal RNA sequencing of the microbiome and enzyme-linked immunosorbent assays on serum or plasma samples.

The data will be analysed using widely used statistical packages Graphpad Prism and Statistical Package for the Social Sciences (SPSS) utilising descriptive statistical tests. Specific techniques may require additional software such as CytoBank for CyTOF data and HistoCAT for imaging mass cytometry.

12. Ethics

The Principal Investigator must ensure that the study will be carried out in accordance with the ethical principles in the Research Governance Framework for Health and Social Care, Second Edition, 2005 and its subsequent amendments as applicable and applicable legal and regulatory requirements.

None of the Investigators declare any conflicts of interest with regards to this study.

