17.1	Adverse Events (AEs).....	21
17.2	Adverse Reaction (ARs).....	21
17.3	Notification and reporting of Adverse Events and Reactions	21
17.4	Serious Adverse Events (SAEs) or reactions	21
17.5	Notification and reporting of Serious Adverse Events.....	21
17.6	Urgent Safety Measures.....	22
17.7	Annual Safety Reporting	22
17.8	Overview of the Safety Reporting responsibilities.....	22
18.	Monitoring and auditing	22
19.	Trial committees	23
20.	Finance and funding	23
21.	Indemnity.....	23
22.	Dissemination of research findings	23
23.	References	24

2. Glossary

AE	Adverse Event
AR	Adverse Reaction
ASR	Annual Safety Report
BMI	Body Mass Index
CAP	Controlled Attenuation Parameter
CI	Chief Investigator
CRF	Case Report Form
CyTOF	Mass Cytometry
FNA	Fine Needle Aspirate
GLP-1	Glucagon Like Peptide 1
HOMA-IR	Homeostatic Model Assessment of Insulin Resistance
HRA	Health Research Authority
JRMO	Joint Research Management Office
NAFLD	Non-alcoholic fatty liver disease
NASH	Non-alcoholic Steatohepatitis
NIHR	National Institute for Health Research
Participant	An individual who takes part in a clinical trial
PI	Principle Investigator
PIS	Patient Information Sheet
REC	Research Ethics Committee
T2DM	Type 2 Diabetes Mellitus

3. Signature page

Chief Investigator Agreement

The study as detailed within this research protocol will be conducted in accordance with the principles of Good Clinical Practice, the UK Policy Framework for Health and Social Care Research, and the Declaration of Helsinki and any other applicable regulations. I agree to take responsibility for the statistical analysis and oversight of this study.

Chief Investigator Name: [name]

Signature:

Date: 04/09/2018

4. Summary and synopsis

Short title	Investigating mechanisms in non-alcoholic fatty liver disease
Methodology	Cross-sectional study
Research sites	Barts Health NHS Trust, Homerton University Hospital NHS Foundation Trust Kings College Hospital, NHS Foundation Trust Bromley by Bow Centre
Objectives / aims	To identify key characteristics of the tissue resident and peripherally circulating immune-phenotype in addition to blood markers, metabolic profile, faecal and oral microbiota in non-alcoholic fatty liver disease within an ethnically diverse population
Number of participants	153

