Inclusion and exclusion criteria	Over 18 years of age Confirmed Non-alcoholic Fatty Liver disease or Healthy Control Excluding participants with type 1 Diabetes Mellitus or immune-suppressant concomitant medication or auto-immune disease or excessive alcohol intake
Statistical methodology and analysis	Comparative and descriptive
Study duration	24 months

5. Introduction

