6.3 Primary endpoint

To determine differences between specific immune cell populations in peripheral blood, liver and adipose tissue between two methods of 5% to 7% weight loss.

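### Does a 24-month study duration that equals the 24-month recruitment period leave late recruits without their final visit?

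*Protocol*

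**What the plan says.** The synopsis (Protocol section 4) carries the line "Study duration 24 months" and describes the methodology as "Cross-sectional study". It does not define study duration or divide it into recruitment and follow-up.

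Section 8 states "We plan to recruit 153 participants over an expected 24 month period". On follow-up it says "All participants will have a final study visit once they have attained 5% to 7% weight loss" and, on timing, "this is expected to be between one to six months after baseline visit". It adds: "Participants who do not achieve at least 5% weight loss 6 months after the baseline visit will also be asked to attend the visit".

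Section 9 is narrower. It offers the follow-up visit to participants with NAFLD, and its visit table lists blood, Fibroscan and an optional liver aspirate at that visit. Section 7 expects most participants to attend only one or two visits. Section 6.3 gives the primary endpoint as "To determine differences between specific immune cell populations in peripheral blood, liver and adipose tissue between two methods of 5% to 7% weight loss".

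**The concern.** The protocol gives 24 months twice, once for recruitment and once for the study as a whole, and then asks for a visit up to six months after enrolment. If all three figures are taken at face value, there is no calendar time for the final visit of the last people recruited.

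The final visit matters. The primary endpoint compares immune cells between two routes to the same weight loss, and the post-weight-loss blood comes from this visit. So does the post-weight-loss liver sample, for those who agree to it; section 10 says "Participants will have an optional fine needle aspiration of their liver at baseline and at follow up, once attaining 5% to 7% weight loss". If the study really stopped at month 24, late recruits would contribute a baseline and possibly no follow-up. The 20% allowance in section 11 is for dropout, not for visits cut off by the calendar.

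**Working it through.** **Inputs from the protocol**
- Study duration: 24 months (section 4).
- Recruitment: 153 participants over an expected 24 months (section 8).
- Baseline to final visit: 1 to 6 months, with those who have not lost 5% also asked to attend at 6 months (section 8).
- Controls: 20 before the 20% allowance (section 11).

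**Assumption.** Enrolment is even over time. The protocol gives no accrual pattern.

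**1. The stated duration.** Duration = recruitment + time to the last final visit.
- No follow-up: 24 + 0 = 24 months. Only this reproduces the synopsis figure.
- Shortest expected follow-up: 24 + 1 = 25 months.
- Longest expected follow-up: 24 + 6 = 30 months, or slightly more if the six-month visit is booked late.

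The synopsis figure therefore matches recruitment alone and is 1 to 6 months short of recruitment plus follow-up.

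**2. Who would be affected by closure at month 24.** This is hypothetical, because the protocol states no such closure. A full six-month window needs enrolment by month 24 − 6 = 18. A one-month visit needs enrolment by month 24 − 1 = 23.

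Counting all 153, as section 8 does, the rate is 153/24 = 6.375 per month:

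| Enrolled in months | Number | Share | Window before month 24 |
|---|---|---|---|
| 0–18 | 18 × 6.375 = 114.75 | 75% | full 6 months |
| 18–23 | 5 × 6.375 = 31.875 | 20.8% | 1 to 6 months |
| 23–24 | 1 × 6.375 = 6.375 | 4.2% | under 1 month |

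About 38 (31.875 + 6.375 = 38.25, 25%) lack the full window.

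Counting only participants with NAFLD, as section 9 does, the number depends on how many of the 153 are controls:
- Section 11's total reproduces as 80/0.75 = 106.7, rounded up to 107; 107 + 20 = 127; 127 × 1.2 = 152.4, rounded up to 153. On that build the controls also carry the allowance: 20 × 1.2 = 24, leaving 153 − 24 = 129 with NAFLD.
- With 20 controls exactly, 153 − 20 = 133 have NAFLD.
- Without a full window: 129 × 6/24 = 32.25 to 133 × 6/24 = 33.25, so about 32 to 33.
- Without room for a one-month visit: 129/24 = 5.4 to 133/24 = 5.5, so 5 or 6 people, again about 4%.

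**3. What these counts do not show.** The visit is triggered by reaching 95% of starting weight, which is expected from one month onward. Someone with a three-month window who reaches the target at two months is seen in time. The protocol gives no distribution of time to 5% loss, so the number of missed visits cannot be estimated. The 25% is a ceiling that would apply only if everyone needed the full six months.

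**4. The cost of fitting everything into 24 months.** Recruitment would have to close at month 18, at 153/18 = 8.5 per month instead of 6.375. The ratio is 8.5/6.375 = 1.33, or one third faster. Section 8 already plans for possible under-recruitment by naming further centres.

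**The case for a change.** The best case for a change is that duration, recruitment period and visit timing are all protocol content, all three are stated, and they do not add up. Correcting them would take one synopsis line and one sentence in section 8. If 24 months were treated as a hard end date, the loss would fall on the visit that supplies the follow-up half of the primary comparison. The cross-sectional label does not rescue the figure, since it too fails to describe a study with a follow-up visit. Restricting follow-up to NAFLD lowers the counts but leaves the 25 to 30 months as they are, unless the last recruits all happen to be controls, which is not planned.

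The mismatch stands: the line is imprecise, and anyone revising the synopsis for another reason could tidy it. The harm does not stand. It needs a closure at month 24 that the protocol nowhere orders, and it sets an undefined synopsis entry above section 8's explicit instruction to see participants up to and at six months. Both the recruitment period and the visit timing are given as expectations, so faster accrual would also remove the overlap.

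**Conclusion.** The arithmetic is right and the consequence is not. The last final visits fall at months 25 to about 30, against a synopsis figure of 24. The simplest reading is that the synopsis gives recruitment time under a loose label, and its cross-sectional description likewise leaves the follow-up out of account. On that reading the figures are compatible.

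No eligibility rule, visit, sample-size step or analysis uses the synopsis duration, so relabelling it would alter no result. Study staff working from section 8 would continue final visits past month 24 and lose none. The other remedy, closing recruitment at month 18, would require accrual one third faster to protect against an event the protocol does not foresee.

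The figures of about 32 to 33 participants with NAFLD (or 38 of 153) without a full window, and about 4% with no room for a one-month visit, rest on even accrual and on closure at month 24. They are not expected losses. This is a clerical imprecision and calls for no change to the plan.

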Apart from performing a liver biopsy, there is no convenient or accurate way to distinguish patients who have NASH from those who have simple steatosis which does not progress. This is largely because the pathogenesis of NASH is not fully understood. Hepatic fat deposition, genetic abnormalities, oxidative stress, inflammatory cytokines and more recently bacterial dysbiosis have all been shown to be relevant, but, the mechanisms that link these phenomena to NASH have not been elucidated^{9,10}. For the same reasons, there are currently no drugs licensed for the treatment of NASH and prevention of its complications. Therefore the cornerstone of treatment is behaviour and lifestyle change, but adherence to such changes is limited and effect on long term outcomes has not been demonstrated.^{11,12} However, public health measures such as education and legislation will take many years to impact on the burden of established liver disease in the population. Therefore, there is a large unmet clinical need for drugs to target the pathogenic processes that drive inflammatory liver diseases.

Therefore, what is needed is a better understanding of the mechanisms that are associated with NASH in order to develop effective biomarkers of disease stage and therapeutic targets. In recent years, it has become clear that NASH is driven by a combination of metabolic dysfunction and an aberrant immuno-inflammatory response resulting in liver cell injury, and fibrosis. In a multisystem disease such as NASH, many tissues are affected and a comprehensive understanding of the disease

cannot take place without simultaneously studying the different tissues involved, including liver, fat tissue, muscle and blood. Historically such co-ordinated tissue assessment has been very difficult, but the recent rise to prominence of bariatric surgery as a metabolic treatment intervention changes that.

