A previous meta-analysis has revealed weight loss improves steatosis and cardio-metabolic risk factors including HOMA-IR, lipid profile and glycated haemoglobin (HbA1c).³⁰ More recently, a cohort study of 293 NASH patients encouraged to adopt lifestyle changes over 52 weeks showed a dose-response between weight loss and all histological parameters of NASH with benefit seen with weight loss greater than 5%.¹²

In this study, we will collect tissue, blood, stool, urine and saliva samples at the same time in order to enable a comprehensive disease phenotyping and ability to compare immunological, microbiological and metabolic features in patients with varying stages of NAFLD and healthy controls. To date there are no published data evaluating simultaneously-obtained samples from adipose, gut and liver tissue and peripheral blood in NAFLD. The important regulatory role of adipose tissue in systemic inflammation has been highlighted previously and demonstrated a hyperactive state

in obesity.^{31,32} Therefore, a significant proportion of the participants in this study will be recruited from the bariatric surgery services so that these multiple tissue samples can be collected at time of surgery with minimal additional risk to participants.

The largest cohort of paired liver biopsies monitoring the effects of weight loss through lifestyle modification revealed that a significantly greater proportion of individuals had histological resolution of NASH if they lost greater than 5% of body weight.¹² Insulin resistance is a key component to NAFLD, therefore, the dramatic impact upon hepatic insulin resistance and gut hormones seen post bariatric surgery may display a very different pathological phenotype compared to the same amount of weight loss attained through lifestyle changes. This study will enable evaluation of these immunological, microbiological and metabolic features of NAFLD at baseline and in participants who have lost at least 5% of body weight by lifestyle interventions versus a bariatric surgery. This comparison may reveal unique insight into the pathological mechanisms in NAFLD altered by the rapid improvement of the metabolic syndrome seen after bariatric surgery independent of the amount of weight loss.

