6.1 Primary objective

To determine the changes in tissue-specific and peripheral immuno-inflammatory and metabolic abnormalities in NALFD in people who achieve 5% to 7% weight loss by Roux-en Y gastric bypass surgery or lifestyle measures.

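### Section 11 sizes the study on fibrosis-stage groups, while the primary comparison is bypass versus lifestyle weight loss: neither arm has a number, and participants without histology reduce the stated 40 per group

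*Protocol*

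**What the plan says.** Section 11 (Statistical considerations) declines a formal power calculation because the work is exploratory. It rests the sample size on earlier work by the group, which suggests that "40 patients in each of the following groups: NASH with mild fibrosis (stages 0-1) and significant fibrosis (stages 2-4) will be informative". It continues: "Given that we cannot determine the stage of disease before surgery, and assuming a conservative NASH rate of 75% of all patients". It then assumes a "relatively even split of patients into the two categories and 20 healthy control participants", and concludes that "we estimate that a total sample size of 153 will enable us to recruit with 20% contingency for dropout".

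The primary objective (6.1) concerns changes "in people who achieve 5% to 7% weight loss by Roux-en Y gastric bypass surgery or lifestyle measures". The primary endpoint (6.3) is a difference in immune-cell populations "between two methods of 5% to 7% weight loss". No section gives a planned number or ratio for either method.

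Section 5.1 also states an aim that stage-based sizing does serve, namely to "compare immunological, microbiological and metabolic features in patients with varying stages of NAFLD and healthy controls".

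On who can be staged, section 5.1 says: "Apart from performing a liver biopsy, there is no convenient or accurate way to distinguish patients who have NASH from those who have simple steatosis". Section 7.1 admits NAFLD on a clinical, radiological or histological diagnosis. Section 5.2 and the visit table in section 9 confine biopsy tissue to planned surgery or a biopsy that is already indicated. Part of the cohort comes from a community weight-loss programme (section 7).

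**The concern.** The sizing argument and the primary comparison divide the participants along different lines. The argument in section 11 treats NAFLD participants as people who will be staged at surgery. The primary comparison needs a lifestyle group, and many of its members may never have liver histology. A lifestyle participant without histology uses a NAFLD place but cannot enter either fibrosis group, so the two aims draw on the same places.

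Two things are at stake. The stated 40 per fibrosis group may not be what the design delivers. And the size of the primary comparison is left to whoever happens to be recruited, because no arm number enters the derivation.

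**Working it through.** **Inputs, all from section 11:** 40 + 40 = 80 staged NASH patients; NASH rate 75%; 20 controls; 20% dropout allowance; total 153.

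**Reproducing 153.** NAFLD patients needed before dropout: 80 / 0.75 = 106.67, or 107 rounded up. Two routes then reach the stated total, and the text does not say which was used.

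- Route A, 20% added to everyone: (107 + 20) x 1.2 = 152.4, rounded up to 153. Controls take 20 x 1.2 = 24, leaving 153 - 24 = 129 NAFLD places. Implied retention is 1/1.2 = 0.833.
- Route B, 20% loss among NAFLD patients only: 106.67 / 0.8 + 20 = 153.3, or 153. This leaves 153 - 20 = 133 NAFLD places with retention 0.8.

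No figure for a weight-loss arm enters either route.

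**Slack on the plan's own inputs.** Expected staged NASH patients if every NAFLD participant can be staged:

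- Route A: 129 x 0.75 / 1.2 = 80.6
- Route B: 133 x 0.75 x 0.8 = 79.8

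The target is 80, so there is essentially no slack.

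**Effect of participants without histology.** Let U be their number. The protocol gives no value, so those below are assumptions. Expected per fibrosis group = (places - U) x 0.75 x retention / 2.

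| U | Route A | Route B |
|---|---|---|
| 0 | 40.3 | 39.9 |
| 20 | 34.1 | 33.9 |
| 40 | 27.8 | 27.9 |

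Every 10 unstaged participants remove 10 x 0.75 x 0.833 = 6.25 (A) or 10 x 0.75 x 0.8 = 6.0 (B) expected staged NASH patients across the two groups.

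**How many unstaged participants fit while keeping 40 + 40.** Break-even U = places - 80 / (NASH rate x retention to staging).

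| NASH rate | Loss before staging | Route A | Route B |
|---|---|---|---|
| 75% | plan's allowance | 1.0 | -0.3 |
| 90% | plan's allowance | 22.3 | 21.9 |
| 75% | none | 22.3 | 26.3 |
| 90% | none | 40.1 | 44.1 |

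The 90% row reflects the figure of almost 90% that section 11 cites from a bariatric cohort. The rows with no loss represent the case where participants leave only after tissue is taken at Visit 2.

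**The case against.** The study is declared exploratory, disclaims formal power and plans descriptive analysis. No error rate or decision rule hangs on 40 + 40. This stands and limits the weight of the point, but it does not explain why the stated rationale addresses a different comparison from the primary one.

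A reader might infer that every lifestyle participant without histology takes a place that 40 + 40 needs. The documents do not support that. Section 11 calls 75% conservative beside a cited figure near 90%. Surgical tissue is taken at Visit 2, so a participant lost between Visit 2 and the final visit is already staged. Nothing says that the whole 20% falls before staging. Some clinic participants may also have histology, since 7.1 allows a histological diagnosis and section 9 allows access to existing surplus tissue.

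A reader might also take the 75% as a bariatric rate wrongly applied to everyone. Section 11 cites both 59.1% for NAFLD generally and almost 90% for a bariatric cohort, and it words the 75% as covering all patients. A blended rate is equally possible, so only clarification can be asked.

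Fibroscan and optional fine needle aspiration are open to lifestyle participants and serve the severity and immune-cell endpoints. By section 5.1, however, they do not identify NASH, which the two groups in section 11 require.

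Arm numbers might be thought a matter for a statistical analysis plan. But they govern recruitment, and section 11 already fixes the sizing on other groups.

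**Conclusion.** The point holds as a correction to the sizing statement. The total of 153 is not an arithmetic error: it reproduces from the fibrosis-group inputs, and only from them. Neither arm of the primary comparison is sized. On the plan's own 75% and 20%, 40 per fibrosis group leaves room for at most one participant without histology. With 20 such participants the expected size is about 34 per group, and with 40 about 28. Under more favourable assumptions about the NASH rate or the timing of losses, 22 to 26 fit, and 40 to 44 if both apply. The number unstaged is an assumption throughout.

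The shortfall falls on the fibrosis-stage comparison. The primary endpoint concerns immune-cell populations and does not require NASH staging, so unstaged participants still count there. For the primary comparison the fault is that its size is unstated. A reader might infer that it will be badly unbalanced or too small; without arm numbers, or a rate of reaching 5% loss, the protocol supports neither conclusion. Section 8 asks those under 5% at six months to attend the final visit, so they are not dropouts in the ordinary sense, and section 11 does not say whether the contingency covers them.

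The point should be fixed but is not fatal.

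**What to change.** Keep 153 and restate section 11:

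1. Give planned numbers for bypass, lifestyle and control participants, and the number of NAFLD participants expected to have histology.
2. Either replace the 40 per fibrosis group with the number expected under that split, presented as a descriptive comparison among participants with histology; or keep 40 + 40 and state the assumed NASH rate, the assumed loss before staging and the limit on unstaged enrolment that follows.
3. State how many in each arm are expected to reach 5% loss for the primary comparison, and whether the 20% contingency covers those who do not.
4. State which population the 75% NASH rate describes.
5. Align the synopsis, which labels the study cross-sectional and gives an aim with no weight-loss comparison, with the longitudinal primary objective.

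The cost is a rewritten section 11 and two synopsis lines, with recruitment tracked by arm. No extra patients are needed. The downside is that either the stated fibrosis-group size becomes less favourable or the lifestyle arm is limited.
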